1.6. Description of the population to be studied

Sixty-four (64) healthy male volunteers, aged 18 to 50 will be included in the study. They will be recruited from volunteers' database of the clinical unit.

Recruitment has been limited to Caucasian population to avoid possible ethnicity differences in assessments within a cohort.

Newspaper advertisements, radio spots, posters, mailing, specific press inserts, broadcast message or clinical unit recruitment website may be used. Only study-specific recruitment tools approved by EC will be used.

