3.2. Design

This will be a First in Human (FiH) phase I blinded, single ascending dose study with DNDI-6148 administered as an oral suspension in healthy male volunteers. Each cohort will include 8 subjects (6 active/ 2 placebo).

Bioanalysis (in plasma and urine) will be performed in open conditions. Central reading for ECGs will be in blind conditions.

[figure not shown]
Decision on dose escalation will be taken in blinded conditions, based on safety interim report and DNDI-6148 plasma exposure.

The administered dose will be 10 mg, 20 mg, 40 mg, 80 mg, 160mg, 260 mg, 380 mg and 500 mg. The treatment will be administered as a single dose on Day 1.

The study plan is shown in Figure 1.

Study procedures are detailed in Section 6 and 7.

Figure 1 Study plan

¹ only for the cohorts $\overline{160}$ mg, $\overline{260}$ mg, $\overline{380}$ mg and $\overline{500}$ mg

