3.3.3. Risk assessment, study conduct and method of dose escalation

3.3.3.1. Number of subjects receiving the study drug simultaneously

To minimize the risk to healthy volunteers, the administration of the investigational product in each dose group of the study will be done sequentially within each cohort:

Table 7 Cohorts and treatment doses.

Cohort	Treatment dose (randomization)
1 (8 subjects)	Single oral administration of DNDI-6148, 10 mg on Day 1 or placebo (6/2)
2 (8 subjects)	Single oral administration of DNDI-6148, 20 mg on Day 1 or placebo (6/2)
3 (8 subjects)	Single oral administration of DNDI-6148, 40 mg on Day 1 or placebo (6/2)
4 (8 subjects)	Single oral administration of DNDI-6148, 80 mg on Day 1 or placebo (6/2)
5 (8 subjects)	Single oral administration of DNDI-6148, 160 mg on Day 1 or placebo (6/2)
6 (8 subjects)	Single oral administration of DNDI-6148, 260 mg on Day 1 or placebo (6/2)
7 (8 subjects)	Single oral administration of DNDI-6148, 380 mg on Day 1 or placebo (6/2)
8 (8 subjects)	Single oral administration of DNDI-6148, 500 mg on Day 1 or placebo (6/2)

At each dose level, subjects will be split at least in two sub-cohorts: first sub-cohort will be one subject under active, one subject on placebo (sentinel approach as recommended by EMA[7]). The 6 remaining subjects will be dosed after a minimum of 24 hours of safety surveillance of the first 2 subjects. Decision to proceed with the administration of the 6 remaining subjects will be taken by the investigator on the basis of biology and clinical safety data. The 6 remaining subjects can be divided in multiple subgroups. Any safety data available on previous subjects will be taken into consideration before dosing any new subject. Any concern should be shared with the Sponsor prior to next dosing.

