3.5. Stopping rules

3.5.1. Trial stopping criteria

The trial will be stopped if either of the following occurs:

- a 'serious' adverse reaction (SAR) (i.e. a serious adverse event (SAE) considered at least possibly related to DNDI-6148) in one subject; or
- 'severe' non-serious adverse reactions (AR) (i.e. severe non-serious adverse events considered as, at least, possibly related to DNDI-6148) in two subjects in the same cohort, independent of within or not within the same system organ class (SOC).

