3.5.3. Dose escalation Stopping criteria between cohorts

The Safety Review Committee will decide to stop the dose escalation as planned per protocol in case of occurrence of:

- 2 subjects of the same cohort experiencing:
 - a significant increase of ALAT > 3ULN,

- simultaneous increases of total bilirubin > 2ULN, ALAT > 2ULN and alkaline phosphatases > 1.5ULN,
- ➤ 6 subjects of the same cohort experiencing:
 - study drug related moderate, non-serious AEs (that are considered at least possibly related to the drug effect i.e. moderate, non-serious ARs).
- 1 subject of the cohort presenting:
 - a C_{max} or AUC₀₋₂₄ value above 7.3 μg/mL and 65 h*μg/mL, respectively (based on the NOAEL in Cynomolgus toxicology studies).
- The maximum C_{max} and AUC_{0-24} observed in the cohort leads to believe that, taking into account the dose increase, C_{max} or AUC_{0-24} values of 7.3 µg/mL and 65 h*µg/mL might be overpassed with the following planned higher dose.

In one of the cases listed above, the dose group in progress will be stopped and the blind could be broken by the investigator or on request of the sponsor, for one or several volunteers, or the Safety Review Committee could request the support of an independent non-blinded external advisor. Regarding laboratory abnormalities described above, if unblinding confirms that at least two subjects presenting these abnormalities received the active drug, the dose escalation will be stopped.

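### Section 3.5.3 gives the laboratory escalation stop two triggers: a blinded count of two subjects in either arm, and an unblinded count of two subjects on active drug

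*Protocol*

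**What the plan says.** Section 3.2 fixes the cohort, "Each cohort will include 8 subjects (6 active/ 2 placebo"), and the conditions of the escalation decision: "Decision on dose escalation will be taken in blinded conditions, based on safety interim report and DNDI-6148 plasma exposure". Section 3.3.3.2 repeats that the safety and PK review is blind.

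Section 3.5.3 then contains three statements that bear on the laboratory criterion:

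- **Opening:** "The Safety Review Committee will decide to stop the dose escalation as planned per protocol in case of occurrence of" the listed events. The first is two subjects of one cohort with either ALAT above 3 ULN or a combined rise in bilirubin, ALAT and alkaline phosphatase. No arm is named.
- **Middle:** in any listed case the dose group under way is stopped. The investigator may break the blind, or the sponsor may ask for this, for one or more volunteers. Alternatively the Committee may seek help from an independent non-blinded adviser. Both are permissions, not requirements.
- **Closing, laboratory abnormalities only:** "if unblinding confirms that at least two subjects presenting these abnormalities received the active drug, the dose escalation will be stopped".

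Section 3.3.3.2 lets the study move to the next dose only if the stopping rules are not met, and rules out duplicating a cohort once they are met. Section 3.7.1 keeps the code from the investigator and the sponsor's trial team except as 3.7.2 allows. Section 3.7.2 covers medical need of the individual subject and, for the sponsor's pharmacovigilance department, a SUSAR.

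**The concern.** A stopping rule in a first-in-human study should give one answer for one set of data. Here the opening counts affected subjects whatever they received, and the closing counts only those confirmed on DNDI-6148. The step that would choose between the two counts is optional. The text is silent on what follows if the blind is kept, or if it is broken and fewer than two affected subjects turn out to have been on active drug.

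Whether the rule counts as met decides whether the next dose level may open and whether the cohort may be duplicated. The Committee could reach either answer from the same liver results and cite 3.5.3 for it. The code-break sections also do not provide for the unblinding on which the closing sentence depends.

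**Working it through.** **Inputs.** 6 active and 2 placebo subjects per cohort (3.2); 8 cohorts (Table 7); a laboratory count of two (3.5.3). The protocol's totals reproduce: 8 × 8 = 64, matching "Sixty-four (64) healthy male volunteers, aged 18 to 50 will be included in the study" in section 1.6; and in 3.3.3.2, 6 complete subjects less at most 2 on placebo leaves the stated minimum of 4 on active. The protocol gives no operating characteristics for its stopping rules, so there is no such figure to reproduce.

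**The sentences applied to exactly two affected subjects in a cohort**

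| Affected subjects | Opening sentence | Closing sentence |
|---|---|---|
| 2 active, blind broken | stop | stop |
| 1 active + 1 placebo, blind broken | stop | condition not satisfied |
| 2 placebo, blind broken | stop | condition not satisfied |
| any split, blind kept | stop | cannot be evaluated |

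Taken literally, the closing sentence gives a sufficient condition for stopping and does not say that escalation otherwise continues. But if two affected subjects in any arm already compel a stop, the closing sentence adds nothing. It has an effect only if it narrows the opening one, and then the two conflict.

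**How often the split matters.** Assume that whether a subject is affected does not depend on arm. With k affected of 8, the probability that a are on active is C(6,a) × C(2,k−a) / C(8,k).

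For k = 2, C(8,2) = 28:

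- both active: C(6,2)/28 = 15/28 = 53.6%
- one of each: 6 × 2/28 = 12/28 = 42.9%
- both placebo: 1/28 = 3.6%

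At least one is on placebo in 12/28 + 1/28 = 13/28 = 46.4%. In these cases the sentences diverge.

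For k = 3 they diverge only when both placebo subjects are affected: C(6,1) × C(2,2)/C(8,3) = 6/56 = 10.7%. For k = 4 or more, at least two affected subjects are always on active, so the counts agree.

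**Illustration with assumed rates.** Take a common per-subject probability p of meeting a liver criterion. The any-arm trigger is P(X ≥ 2) with X ~ Bin(8, p); the active-only trigger uses Bin(6, p).

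| Assumed p | ≥ 2 of 8, any arm | ≥ 2 of 6, active only |
|---|---|---|
| 1% | 0.27% | 0.15% |
| 2% | 1.03% | 0.57% |
| 5% | 5.7% | 3.3% |
| 10% | 18.7% | 11.4% |

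These are per-cohort figures. They compare the two counting bases and do not predict what will happen in this trial.

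**Access to the code.** Section 3.5.3 allows unblinding by the investigator or at the sponsor's request after a stopping criterion. Section 3.7.1 refers all such access to 3.7.2, whose grounds do not include a stopping rule.

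**The case against.** The strongest reply is that 3.5.3 describes a sequence: a blinded count is the trigger, the dose group is stopped, the blind may then be broken, and for laboratory findings confirmation on active makes the stop firm. This is plausible and may well be what was meant. It also answers any worry that dosing continues while the matter is open. What it does not settle is the outcome. The opening sentence is worded as a decision to stop escalation, not as a pause. The confirming step is not required, and nothing says what follows when it is omitted or shows fewer than two on active.

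The 46% is also conditional on two subjects being affected and on arm playing no part. It is not the probability of an unnecessary stop. That limit stands.

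A reader might go further and infer that the adverse-event stops are faulty too, because they carry no confirmation of active treatment and placebo events could halt the trial. The documents do not support this. The adverse-reaction stop in 3.5.1 ("in two subjects in the same cohort, independent of within or not within the same system organ class (SOC")), the severe-event count in 3.5.2 and the count of "study drug related moderate, non-serious AEs" in 3.5.3 are limited to events judged at least possibly related. The ALAT count in 3.5.2 has no such filter, but no passage says that it, or any of the others, counts active subjects only, so there is no second statement to contradict. Acting on blinded counts is a legitimate cautious choice, in keeping with section 8.4, which stops all dosing after any SAE, related or not. High percentages for placebo involvement in those counts follow almost automatically from having two placebo subjects per cohort and a sentinel pair made up of "first sub-cohort will be one subject under active, one subject on placebo"; they do not show a defect.

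**Conclusion.** The point holds for the laboratory criterion of 3.5.3. Its opening and closing sentences use different counting bases, the step between them is optional, and 3.7.1 and 3.7.2 do not provide for it. The conflict arises when exactly two subjects are affected with at least one on placebo, or when three are affected including both placebo subjects. Given the affected number, and if events are unrelated to arm, that is 46% and 11% of such cases respectively. How often two or three subjects would be affected cannot be known from the protocol.

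The consequence is limited, because the dose group is stopped in the meantime. It is still real, because the status of the rule governs both escalation and cohort duplication under 3.3.3.2. The inconsistency itself is visible in the text and needs no assumption.

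**What to change.** Reconcile the opening and closing sentences of 3.5.3 for the laboratory criterion:

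1. State one counting basis: all subjects in the cohort, or subjects confirmed on active drug.
2. State whether unblinding, or review by the non-blinded adviser already foreseen there, is part of the rule or only an option.
3. State what follows for escalation, and for whether the rule counts as met under 3.3.3.2, if unblinding is not done or shows fewer than two affected subjects on active.
4. Align 3.7.1 and 3.7.2 with whatever unblinding 3.5.3 allows, including who may do it.

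The choice of basis is a clinical decision for the sponsor, and this review takes no position on it. The cost is a protocol wording change and, if confirmation is made a requirement, a short pause while it is obtained.

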3.5.4. Restarting the trial

If, after consultation of the Safety Review Committee, it is appropriate to restart the trial, a substantial amendment will be submitted to the Health Authorities and Ethics Committee. The trial will not restart until the amendment has been approved by the Health Authorities and Ethics Committee.

3.6. Removal of Subjects from Therapy or Assessment

In accordance with the Declaration of Helsinki, subjects will be free to withdraw from the study at any time if they wish to do so, for any reason, specified or unspecified.

Subjects who withdraw from trial participation before randomization are considered screening failures.

The following reasons will be accepted for study discontinuation:

- Withdrawal of subject consent, or loss to follow-up, or inability to remain under medical observation including post-study examination,
- Non-compliance or major deviation from the protocol,
- Appearance of a serious AE (SAE),
- New significant information (French regulation: "fait nouveau"), any new fact concerning the research or the study product which may jeopardize the participants' safety, and which leads the Sponsor or Investigator to take appropriate urgent security decision,
- Any other situation where, in the opinion of the Investigator, continuation of the study would not be in the interest of the subject,
- Discontinuation of the study by the Sponsor.

Should any of the subjects be withdrawn from the study, the Sponsor's representative and Investigator will discuss the possibility of replacement. All subjects withdrawing for reasons unrelated to the investigational product will have to be replaced. The reason for withdrawal will have to be recorded in the e-CRF for all withdrawn subjects.

The e-CRF has to be completed up to the time of drop out. All drop outs after the first intake of investigational product should be given a post-study assessment as appropriate. The premature termination form in the e-CRF must be completed for all drop outs.

All data, including any drug concentrations from any withdrawn subject, have to be included in the final clinical study report. These data will only be evaluated if both the Sponsor and the Investigator agree that it is valid to do so.

Subjects presenting adverse experiences will undergo a physical examination and laboratory tests planned at the subsequent visits. A follow-up of AEs will also be undertaken for all subjects until resolution or stabilisation of the event.

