2. STUDY OBJECTIVES AND PURPOSE

2.1. Primary objective

To assess the safety and tolerability of DNDI-6148 after single oral doses administered as oral suspension of DNDI-6148 in healthy male subjects, compared to matching placebo.

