11. STATISTICS

11.1. Description of the statistical methods

The statistical analysis will consist of individual data listings and descriptive statistics performed by EUROFINS OPTIMED (baseline characteristics, safety and study conduct), using the SAS[®] computer program (release 9.4).

The pharmacokinetic and pharmacodynamic data will be analysed by PhinC Development.

All individual data for all included subjects will be presented in data listings, sorted by subject within dose group.

Demographic and baseline characteristics data will be summarized by dose group and overall. On-product/treatment data will be summarized by dose group and overall.

For safety parameters with evaluation before dosing and in case of rechecked value(s) for one subject, only the last observation will be used in descriptive statistics and derivations of other parameter values. After dosing, only observations planned in the protocol will be used in descriptive statistics.

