11.1.2. Analysis of principal criteria

11.1.2.1. Adverse event

AEs will be coded according to the most recent version at the time of study start of the Medical Dictionary for Regulatory Activity (MedDRA). They will be classified into pre-defined standard categories according to chronological criteria:

- Treatment emergent AEs (TEAE): AEs that occurs for the first time or if present before worsened during an exposure to drug(s).

- Non-treatment emergent AEs (NTEAE): AEs that occurs before the study drug administration (also called "pre-dose event").

An AE occurring during the follow-up will be related to the last day of treatment administration received. AEs will be individually listed per subject number, presenting: assigned dose group, verbatim, MedDRA Primary System Organ Class, MedDRA Preferred Term, treatment-emergence (TEAEs or not=NTEAEs) date and time of onset, date and time of last study drug administration before AE, duration, time from onset since last study drug administration, frequency, severity and seriousness, relationship to study drug (with justification is assessed related), the required action taken (e.g. corrective treatment, hospitalisation) outcome and if it is a reason for drop-out.

The non-treatment emergent AEs will be summarised by System Organ Class and Preferred Term for the safety set.

The treatment emergent AEs will be summarised by Primary System Organ Class, Preferred Term and dose group for the safety set. It will consist in the evaluation of the number of AEs and the number of subjects reporting these AEs.

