11.7. Selection of subjects to be included in the analyses

In case of incorrect treatment assigned, subjects will be analysed in the treatment group they actually were included and the treatment they received.

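### Section 3.6 lets a dosed subject who withdrew because of an adverse event be left out of the final safety summaries, at the Sponsor's and Investigator's discretion and with no criterion or timing

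*Protocol*

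**What the plan says.** Two consecutive sentences in section 3.6 govern the data of subjects who withdraw. The first concerns reporting: "All data, including any drug concentrations from any withdrawn subject, have to be included in the final clinical study report". The second concerns analysis: "These data will only be evaluated if both the Sponsor and the Investigator agree that it is valid to do so". The accepted reasons for discontinuation in the same section include a serious adverse event and any situation in which the Investigator thinks that continuing is against the subject's interest. They also include reasons unrelated to harm, such as loss to follow-up, non-compliance and discontinuation by the Sponsor.

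The primary objective (section 2.1) begins: "To assess the safety and tolerability of DNDI-6148 after single oral doses", and the comparison is with placebo. For adverse events, section 11.1.2.1 states: "The treatment emergent AEs will be summarised by Primary System Organ Class, Preferred Term and dose group for the safety set". Section 11.7, on which subjects enter the analyses, has one rule: "In case of incorrect treatment assigned, subjects will be analysed in the treatment group they actually were included and the treatment they received".

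**The concern.** The second sentence of 3.6 makes evaluation conditional. Both parties must agree before the data are evaluated, so non-evaluation is the default and either party alone can block it. The subject of the sentence is all data of a withdrawn subject. Drug concentrations are named only as one part, so safety data are covered.

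In a first-in-human trial the final safety result is a set of counts and descriptive statistics by dose group. If a dosed subject who left because of an adverse event is not evaluated, the incidence at that dose is understated. The decision would be taken with knowledge of the subject's events, and nothing requires it to be taken without knowledge of treatment. The same discretion covers PK, where a withdrawn subject's exposure could be left out of the summaries and the dose-proportionality model without a stated reason.

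**Working it through.** **Does another rule override section 3.6?**

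- Section 11.1.2.1 summarises treatment-emergent events for the safety set with no agreement condition, but the protocol does not define that set. Leaving the definition to the SAP is normal and is not criticised here. It does mean that the protocol nowhere guarantees that every dosed subject is in the summaries.
- Section 11.7 deals only with incorrect treatment.
- Section 11.1 says "After dosing, only observations planned in the protocol will be used in descriptive statistics". This governs which observations count, not which subjects.
- Section 11.1 also says "All individual data for all included subjects will be presented in data listings, sorted by subject within dose group". This covers listings, not summaries.
- Section 4.6.1 allows the Sponsor to keep using data collected before consent is withdrawn. That is a permission, not a commitment to analyse.
- Section 11.1.3 requires the PK SAP to be validated before unblinding. No matching requirement is attached to the agreement in 3.6.

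Nothing overrides the sentence. It is the only explicit rule on evaluating withdrawn subjects' data, and a SAP that analysed every dosed subject unconditionally would depart from it.

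**What lies outside its reach?**

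- Section 3.6 and the listings rule keep the subject in the study report.
- Section 8.4 requires serious events to be notified at once and dosing to be halted, whatever is later evaluated.
- Section 3.3.3.2 requires escalation decisions to use all safety data available at the meeting.
- Sections 3.3.2 and 3.7.1 keep Sponsor and Investigator blinded during the trial. Sections 3.7.2 and 3.5.3 allow the code to be broken in an emergency or when an escalation stopping criterion is met.

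What remains exposed is the final summary tables and the PK summaries.

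**Illustration of size.** Inputs: 8 cohorts of 6 active and 2 placebo subjects (sections 3.2 and 3.3.3.1). The planned total is reproduced: 8 × (6 + 2) = 64, of whom 8 × 6 = 48 are active. The protocol states no withdrawal rate, so the number of subjects leaving because of an event is assumed, and no other event is assumed in the group shown.

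| Assumed withdrawals with an event | All dosed subjects evaluated | Those subjects left out |
|---|---|---|
| 1 in one active dose group | 1/6 = 16.7% | 0/5 = 0% |
| 2 in one active dose group | 2/6 = 33.3% | 0/4 = 0% |
| 1 among all active subjects | 1/48 = 2.1% | 0/47 = 0% |
| 3 among all active subjects | 3/48 = 6.3% | 0/45 = 0% |

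For scale only, the exact (Clopper-Pearson) 95% interval is 0.4% to 64.1% for 1/6. For 0/5 the upper limit is 1 − 0.025^(1/5) = 52.2%. The protocol plans no interval on adverse-event incidence. The practical change is that a dose group that shows an event would show none.

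**The case against.** The strongest reply is that the sentence is loose wording in a descriptive Phase 1 protocol with good safeguards around it. No event can disappear from the record. The adverse-event listing in section 11.1.2.1 even records whether an event was a reason for drop-out, which suggests that the authors expected such subjects in the analysis. A specific statistical section could be read as prevailing over a general paragraph on withdrawal. The SAE case is the least exposed: any SAE is notified immediately and halts dosing (section 8.4), and one related SAE stops the trial (section 3.5.1). With a single dose and residence to Day 4, data up to departure will exist. Both decision-makers are blinded during the trial, and section 13.4 has deviations notified no later than the blind review. PK exclusion criteria belong in the PK SAP.

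Most of this stands, and it limits the consequence. It does not remove the rule. The drop-out field belongs to a listing, and a listing does not correct a summary that omits the subject. Nothing says which section prevails. Blinding reduces the risk, but the decision is not tied to it. A PK SAP can set criteria, but 3.6 would still put an unconditioned agreement beside them.

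A reader might infer from 3.6 that harmed subjects will be excluded, that their events can be hidden, or that escalation could proceed on censored data. The documents support none of these: the rule permits non-evaluation without requiring it, reporting and listing are mandatory, and escalation uses all available safety data. A reader might also carry the illustration to 0/6 by assuming that the harmed subject is replaced. That is not well supported. Section 3.6 leaves replacement of any withdrawn subject open to discussion, but section 4.6.2 provides for it only when the reason is unrelated to the product.

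**Conclusion.** The point holds in limited form. Section 3.6 fixes badly a question that the protocol need not have left to discretion: whether withdrawn subjects' safety data count in the primary safety summaries. It gives no criterion or timing and is not reconciled with section 11.1.2.1. The exposure is confined to the final dose-group summaries and the PK evaluation.

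With 6 active subjects per dose, one omission can take a dose group from 1/6 (17%) to 0/5. That figure rests on an assumed withdrawal and on agreement being withheld; the protocol predicts neither. Given the safeguards, the severity is moderate. The correction is still worth making, because the bias it prevents would fall on the primary objective.

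**What to change.** Replace the conditional sentence in section 3.6 with wording such as:

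*All safety data of every subject who received study drug, withdrawn or not, are included in the safety analyses up to last contact. PK profiles or parameters are excluded only under criteria fixed in the SAP, applied and documented before unblinding.*

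The preceding sentence, on inclusion in the study report, can stay. In the same amendment, reconcile the replacement wording in section 3.6 with section 4.6.2, so that it is clear when a withdrawn subject may be replaced and that a replacement never displaces the original subject's safety data.

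The cost is one sentence plus a consistency edit. It needs no new data, no further subjects and no change to clinical procedures. The Sponsor and Investigator lose only a discretion over safety data for which the protocol gives no reason.
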